### **7.3 Labeling**

Labels will be prepared in accordance with Good Manufacturing Practice (GMP) and local regulatory guidelines. The labels will fulfill GMP Annex 13 requirements for labeling. Label text will be translated into local language, as required. Durvalumab and tremelimumab will be provided with either single-panel labels or multi-language booklet labels.

Label text prepared for durvalumab will show the product name as “MEDI4736” or “durvalumab (MEDI4736)” depending on the agreed product name used in the approved study master label document. All naming conventions are correct during this transitional period.

### **7.4 Storage**

The Investigator, or an approved representative (eg, pharmacist), will ensure that durvalumab and tremelimumab are stored in a secured area, in refrigerated temperatures (2°C to 8°C), and in accordance with applicable regulatory requirements. Sorafenib should be stored according to the Summary of Product Characteristics (“do not store over 25°C). A temperature log will be used to record the temperature of the storage area. Temperature excursions outside the permissible range listed in the clinical supply packaging are to be reported to the monitor upon detection. A calibrated temperature monitoring device will be used to record the temperature conditions in the drug storage facility. Storage conditions stated in the IB may be superseded by the label storage.

## **7.5 Compliance**

The administration of all study drugs should be recorded in the appropriate sections of the eCRF.

Treatment compliance will be assured by reconciliation of site drug accountability logs.

## **7.6 Accountability**

The study drugs provided for this study will be used only as directed in the study protocol.

The study personnel will account for all study drugs dispensed to and returned from the patient.

Study site personnel will account for all study drugs received at the site, unused study drugs, and for appropriate destruction. Certificates of delivery, destruction, and return should be signed.

## **7.7 Concomitant medications and other treatments**

The Investigator must be informed as soon as possible about any medication taken from the time of screening until 3 months after the last dose of study drug(s). Any concomitant medication(s), including herbal preparations, taken during this time will be recorded in the eCRF.

Patients must be instructed not to take any medications, including over-the-counter products, without first consulting with the Investigator.

Restricted, prohibited, and permitted concomitant medications are described in [Table 10](#) and [Table 11](#) (refer also to Toxicity Management Guidelines) For patients randomized to the sorafenib [\[REDACTED\]](#) mg [\[REDACTED\]](#) arm, please refer to the local prescribing information with regards to warnings, precautions, and contraindications.

**Table 10      Prohibited concomitant medications**

Prohibited medication/class of drug:	Usage:
For all treatment arms	
Any investigational anticancer therapy other than those under investigation in this study	Should not be given concomitantly while the patient is on study drug(s)
mAbs against CTLA-4, PD-1, or PD-L1 other than those under investigation in this study	Should not be given concomitantly while the patient is on study drug(s)
Any concurrent chemotherapy, radiotherapy, immunotherapy, or biologic or hormonal therapy for cancer treatment other than those under investigation in this study	Should not be given concomitantly while the patient is on study drug(s). (Concurrent use of hormones for non-cancer-related conditions [eg, insulin for diabetes and hormone replacement therapy] is acceptable. Local treatment of isolated lesions, excluding TLs, for palliative intent is acceptable [eg, by local surgery or radiotherapy].)
Live attenuated vaccines	Should not be given through 30 days after the last dose of study drug(s)
For all immunotherapy arms	
Immunosuppressive medications including, but not limited to, systemic corticosteroids at doses exceeding 10 mg/day of prednisone or equivalent, methotrexate, azathioprine, and tumor necrosis factor- $\alpha$ blockers	
Should not be given concomitantly or used for premedication prior to infusions. The following are allowed exceptions:
 
 
• Use of immunosuppressive medications for the management of study drug(s)-related AEs
 
• Use in patients with contrast allergies
 
• Use of inhaled, topical, and intranasal corticosteroids
 
 
A temporary period of steroids will be allowed if clinically indicated and considered to be essential for the management of non-immunotherapy-related events experienced by the patient (eg, chronic obstructive pulmonary disease, radiation, nausea).

Drugs with laxative properties and herbal or natural remedies for constipation	Should be used with caution through to 90 days after the last dose of tremelimumab during the study
Sunitinib	Should not be given concomitantly or through 90 days after the last dose of tremelimumab (acute renal failure has been reported with combination therapy of tremelimumab and sunitinib)

Prohibited medication/class of drug:	Usage:
EGFR TKIs	Should not be given concomitantly Should be used with caution in the 90 days after last dose of durvalumab Increased incidences of pneumonitis (with third generation EGFR TKIs) and increased incidence of transaminase increases (with 1 st generation EGFR TKIs) has been reported when durvalumab has been given concomitantly.
Herbal and natural remedies, which may have immune-modulating effects	Should not be given concurrently unless agreed by AstraZeneca
AE Adverse event; CTLA-4 Cytotoxic T-lymphocyte-associated antigen-4; EGFR TKI Epidermal growth factor receptor tyrosine kinase inhibitor; mAb Monoclonal antibody; PD-1 Programmed cell death-1; PD-L1 Programmed cell death ligand 1; TL target lesion.	

**Table 11 Supportive medications**

Supportive medication/class of drug:	Usage:
Concomitant medications or treatments (eg, acetaminophen or diphenhydramine) deemed necessary to provide adequate prophylactic or supportive care, except for those medications identified as “prohibited,” as listed above	To be administered as prescribed by the Investigator
Best supportive care (including antibiotics, nutritional support, correction of metabolic disorders, optimal symptom control, and pain management [including palliative radiotherapy to NTLs, etc])	Should be used, when necessary, for all patients
Inactivated viruses, such as those in the influenza vaccine	Permitted

NTL Non-target lesion.

### 7.7.1 Other concomitant treatment

Other medication other than that described above, which is considered necessary for the patients’ safety and wellbeing, may be given at the discretion of the Investigator and recorded in the appropriate sections of the eCRF.

### 7.7.2 Durvalumab drug-drug interactions

There is no information to date on drug-drug interactions with durvalumab either nonclinically or in patients. As durvalumab is a mAb and therefore a protein, it will be degraded to small peptides and amino acids and will be eliminated by renal and reticuloendothelial clearance. It is, therefore, not expected that durvalumab will induce or inhibit the major drug metabolizing

cytochrome P450 pathways. As a result, there are no expected PK drug-drug interactions. The mechanism of action of durvalumab involves binding to PD-L1; therefore, significant pharmacodynamic drug interactions with the commonly administered concomitant medications are not expected. Despite this, appropriate clinical monitoring in all of the planned clinical studies will be conducted to evaluate any potential drug-drug interactions.

## **7.8 Post Study Access to Study Drug(s)**

After the final analysis, AstraZeneca will continue to supply open-label drug to patients per their assigned study treatment until confirmed PD, unacceptable toxicity, or any of the discontinuation criteria are met (see Section 7.2).

# **8. STATISTICAL ANALYSES BY ASTRAZENECA**

## **8.1 Statistical considerations**

All statistical analyses will be performed by AstraZeneca or its representatives.

A comprehensive statistical analysis plan (SAP) will be prepared and signed off before enrollment of the first patient, and any subsequent amendments will be documented, with final amendments completed prior to reporting of the data. In the event a dosing arm is discontinued from the study, it is planned that data from this arm will still be presented in the final study reporting as per the SAP. The primary objective of this study is to assess the efficacy of Arm C vs. Arm D for Overall Survival (OS, for superiority). The key secondary objectives of this study are to assess the efficacy of Arm A vs. Arm D for OS (for non-inferiority, then for superiority). Efficacy data for Arm B (which was closed for enrollment with Amendment 4) will be summarized descriptively, but will not be formally analyzed.

## **8.2 Sample size estimate**

The study will plan to screen approximately 1650 patients in order to randomize approximately 1310 eligible patients in the global study. (This includes 1155 patients randomized to Arms A, C, D with 385 per arm; and approximately 155 patients in Arm B, randomized prior to the closure of this arm. Patients from China enrolled in the global study are included in this figure). Once global enrolment has completed, recruitment into an expansion cohort will continue in China (ie. China Tail) until a total of 180 Chinese patients have been randomized. Patients from China enrolled in the global study and the China Tail will be included in a China cohort. Details of the China cohort and analysis plan will be outlined in a China specific amendment and SAP. Patients will be randomized 1:1:1:1 to durvalumab [redacted] mg monotherapy (Arm A), durvalumab [redacted] mg plus tremelimumab [redacted] mg [redacted] combination therapy (Arm B), durvalumab [redacted] mg plus tremelimumab [redacted] mg [redacted] combination therapy (Arm C), or sorafenib [redacted] mg [redacted] (Arm D). Following Amendment 4 Arm B will be closed for enrollment therefore new patients will be randomized in a 1:1:1 ratio into Arm A, Arm C, and Arm D.

The study is sized to characterize the OS benefit of Arm C vs. Arm D.

The sample size estimation assumes an exponentially distributed OS and a 2-month delay in separation of the OS curves for Arm C vs. Arm D, hence the use of average HR (0.70 for Arm C vs. Arm D). A non-uniform accrual (weight=2) of patients with a duration of 22 months is assumed when estimating the analysis times with a follow-up duration of 15.5 months and a total duration of 37.5 months. No adjustment has been included for dropouts.

For the efficacy comparisons, the median OS for sorafenib (Arm D) is assumed to be 11.5 months, with an 18-month OS rate of 33.8%.

***Durvalumab [REDACTED] mg plus tremelimumab [REDACTED] mg [REDACTED] (Arm C) versus sorafenib [REDACTED] mg [REDACTED] (Arm D) - OS in FAS intent-to treat (ITT)***

The assumed OS treatment effect is an average HR of 0.70 for Arm C versus Arm D. This translates to an increase in median OS from 11.5 months to 16.5 months and in the 18-month OS rate from 33.8% to 46.8% in Arm C versus Arm D.

At the time of the second Interim Analysis (IA2), the analysis of OS will be performed when approximately 404 OS events in Arm C and Arm D combined (~52% maturity) have occurred, approximately 30 months after the first patient is randomized. This number of OS events will provide 85% power to demonstrate a statistically significant difference in OS at a 2-sided 2.22% significance level.

Final analysis of OS will be performed when approximately 515 events in Arm C and Arm D combined (~67% maturity) have occurred, approximately 37.5 months after the first patient is randomized. This number of OS events will provide 97% power to demonstrate a statistically significant difference in OS at a 2-sided 4.25% significance level. The smallest treatment difference that could be observed as statistically significant at the final analysis is an average HR of 0.84 (an increase in median OS from 11.5 months to approximately 13.7 months in Arm C versus Arm D).

***Durvalumab [REDACTED] mg monotherapy (Arm A) versus sorafenib [REDACTED] mg [REDACTED] (Arm D) - OS in FAS ITT***

It is estimated that approximately 453 and 560 events can be observed at the time of the interim and final analysis respectively. The power of the NI test at margin of 1.08 is approximately 84% at final analysis.

- The noninferiority margin of HR 1.08 is determined using 95%-95% fixed margin approach (FDA Guidance 2016; EMEA Guideline 2005) based on two phase 3 trials of sorafenib (Llovet 2008 and Cheng 2009) in first line HCC and assuming conservative 60% retention. Multiple historical trials in the same indication were also designed as NI

- using including Brivanib (Johnson 2013), Sunitinib (Cheng 2013), Linifanib (Cainap 2014), and Lenvatinib (Kudo 2017).

### 8.3 Definitions of analysis sets

Definitions of the analysis sets for each outcome variable are provided in [Table 12](#).

**Table 12 Summary of outcome variables and analysis populations**

Outcome variable	Populations
Efficacy data	
OS	FAS (ITT population)
ORR, BoR, DoR, DCR, DCR-16w, DCR-24w PFS, TTP, OS18, OS24, OS36 and PROs	FAS (ITT population) DoR will be based on the subset of patients in the full analysis set who achieved objective tumor response.
Demography	FAS set (ITT population)
PK data	PK analysis set
Immunogenicity data	
Immunogenicity data	Listings will be based on safety analysis set Summaries will be based on ADA evaluable set
Safety data	
Exposure	Safety analysis set
AEs	Safety analysis set
Laboratory measurements	Safety analysis set
Vital signs	Safety analysis set

AE Adverse event; BoR Best objective Response; DCR Disease control rate; DCR-16w DCR at 16 weeks; DCR-24w DCR at 24 weeks; DoR Duration of response; FAS full analysis set; ITT Intent-to-treat; ORR Objective response rate; OS Overall survival; OS18 Overall survival at 18 months; OS24 Overall survival at 24 months; Overall survival at 36 months, PFS Progression-free survival; PK Pharmacokinetics; PRO Patient-reported outcome; TTP Time to progression.

#### 8.3.1 Full analysis set

The FAS will include all randomized patients. The FAS will be used for all efficacy analyses (including PROs). Treatment arms will be compared on the basis of randomized study drug(s), regardless of the study drug(s) actually received. Patients who were randomized but did not subsequently go on to receive study drug(s) are included in the analysis in the treatment arm to which they were randomized.

### **8.3.2 Safety analysis set**

The safety analysis set will consist of all patients who received at least 1 dose of study drug(s). Safety data will not be formally analyzed but summarized using the safety analysis set according to the study drug(s) received, that is, erroneously treated patients (eg, those randomized to treatment A but actually given treatment B) will be summarized according to the study drug(s) they actually received.

### **8.3.3 PK analysis set**

The PK analysis set will include all patients who receive at least 1 dose of study drug(s) per the protocol for whom any postdose data are available.

### **8.3.4 ADA evaluable set**

The ADA evaluable set will include all patients who have non-missing baseline ADA and at least 1 non-missing post-baseline ADA results. All major ADA analyses will be based on the ADA evaluable set.

## **8.4 Outcome measures for analyses**

### **8.4.1 Calculation or derivation of efficacy variables**

#### **8.4.1.1 RECIST 1.1-based endpoints**

Analysis of the secondary endpoints, ORR, DCR, DCR-16w, DCR-24w DoR, TTP, and PFS, will be based on the Investigator assessments using RECIST 1.1.

#### ***Blinded Independent Central Review (BICR)***

A BICR of radiological scans will be performed on patients included for the first interim analysis, ie, all randomized patients who have had at least 32 weeks of follow-up at the time of the interim analysis 1 (IA1) DCO (ie. randomized  $\geq$  32 weeks prior to IA1 DCO).

The imaging scans will be reviewed by 2 primary radiologist reviewers using RECIST 1.1. If the overall timepoint assessments differ at any timepoint between the 2 primary reviewers, the case will be adjudicated by a third radiologist, who must choose all the overall timepoint assessments from the primary reviewer with which he agrees more. If the overall timepoint assessments are identical between the 2 primary reviewers, the timepoint responses from the reviewer who completed their assessment of baseline scans first will be used for the analyses. For each patient, the BICR will define the overall visit response data (CR, PR, SD, PD, or NE) and the relevant scan dates for each time point (ie, for visits where response or progression is or is not identified).

Further details of the BICR will be documented in the Imaging Charter.

### ***Investigator RECIST 1.1-based assessments***

All RECIST 1.1 assessments, whether scheduled or unscheduled, will be included in the calculations. This is also regardless of whether a patient discontinues study treatment or receives another anticancer therapy.

At each visit, patients will be programmatically assigned a RECIST 1.1 visit response of CR, PR, SD, or PD depending on the status of their disease compared with baseline and previous assessments. Baseline will be assessed within the 28 days prior to randomization. If a patient has had a tumor assessment that cannot be evaluated, then the patient will be assigned a visit response of NE, unless there is evidence of progression in which case the response will be assigned as PD.

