#### **8.4.1.3 Secondary endpoints**

##### ***Objective response rate***

ORR (per RECIST 1.1 as assessed by the Investigator) is defined as the number (%) of patients with at least 1 visit response of CR or PR. Data obtained up until progression, or the last evaluable assessment in the absence of progression, will be included in the assessment of ORR. Patients who go off treatment without progression, receive a subsequent therapy, and then respond will not be included as responders in the ORR.

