##### ***Duration of response***

DoR (per RECIST 1.1 as assessed by the Investigator) will be defined as the time from the date of first documented response until the first date of documented progression or death in the absence of disease progression (ie, date of PFS event or censoring – date of first response +1). The end of response should coincide with the date of progression or death from any cause used for the RECIST 1.1 PFS endpoint.

DoR will not be defined for those patients who do not have documented response.

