##### ***Disease control rate***

DCR (per RECIST 1.1 as assessed by the Investigator) is defined as the rate of best objective response of either CR, PR, or SD according to RECIST 1.1.

DCR-16w is defined as the percentage of patients who have a best objective response of CR or PR or who have SD for at least 16 weeks (-7 days), following the start of study treatment. DCR-24w is defined as the percentage of patients who have a best objective response of CR or PR or who have SD for at least 24 weeks (-7days), following the start of treatment.

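### Section 8.4.1.1 counts all scans regardless of later anticancer therapy, but only ORR excludes responses after such therapy, so best response, DCR-16w and DCR-24w can disagree with ORR

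*Protocol*

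**What the plan says.** Section 8.4.1.1 names the endpoints it governs: "Analysis of the secondary endpoints, ORR, DCR, DCR-16w, DCR-24w DoR, TTP, and PFS, will be based on the Investigator assessments using RECIST 1.1". Under its heading on Investigator assessments it includes all scheduled and unscheduled assessments in the calculations and adds: "This is also regardless of whether a patient discontinues study treatment or receives another anticancer therapy". It makes no reservation for any endpoint.

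Section 8.4.1.3 then defines the endpoints one by one:

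- **ORR.** "Data obtained up until progression, or the last evaluable assessment in the absence of progression, will be included in the assessment of ORR". And: "Patients who go off treatment without progression, receive a subsequent therapy, and then respond will not be included as responders in the ORR".
- **DCR.** It "is defined as the rate of best objective response of either CR, PR, or SD according to RECIST 1.1". No minimum duration of SD is given.
- **DCR-16w and DCR-24w.** "DCR-16w is defined as the percentage of patients who have a best objective response of CR or PR or who have SD for at least" a fixed period, which for DCR-16w is 16 weeks less 7 days. DCR-24w is worded the same way for 24 weeks. Neither mentions subsequent therapy.
- **DoR.** It starts at the first documented response and must end on the date used for PFS. "DoR will not be defined for those patients who do not have documented response".
- **PFS.** It is counted whether or not another anticancer therapy starts before progression.

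Elsewhere, section 5.1 and section 7.2.1.3 keep scanning patients who stop treatment or start another therapy before progression. Section 5.1 describes best response as a response to the study treatment. Section 8.5.3.3 tabulates best response by category and states no data window. Table 12 and section 8.5.3.5 restrict DoR to responding patients.

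**The concern.** The general rule and the ORR rule treat the same scans differently, and the general rule is left standing for the other response endpoints. Because scanning continues after a switch, the scans that cause the disagreement will be in the database.

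Two things are at stake. First, internal consistency: CR plus PR in the best-response table need not equal the ORR responder count, although a reader of the report would expect it to. Second, interpretation: DCR-16w and DCR-24w can contain control achieved under a drug that is not part of the randomised regimen. The trial is open-label, and section 1.2 cites different safety profiles of the immunotherapies and sorafenib, so early switching could differ by arm. Section 2.3 frames these endpoints as Arm A vs. Arm D and Arm C vs. Arm D, and section 8.5.6.2 plans to compare them between Arm C and Arm D in subgroups.

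**Working it through.** The plan states no figure on this point, so there is nothing to reproduce. The check applies the written definitions to four hypothetical patients on the 8-weekly scan schedule of section 5.1. None has progressed when the other therapy starts.

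- **P:** SD at week 8, switches before week 16, PR at week 16.
- **Q:** SD at week 8, switches before week 16, SD through week 24.
- **R:** switches before the week 8 scan, SD at week 8.
- **S:** PR at week 8, switches, progresses later.

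| | P | Q | R | S |
|---|---|---|---|---|
| ORR (8.4.1.3) | No | No | No | Yes |
| Best response, all scans (8.4.1.1) | PR | SD | SD | PR |
| Best response, scans before switch | SD | SD | NE | PR |
| DCR, all scans | Yes | Yes | Yes | Yes |
| DCR, scans before switch | Yes | Yes | No | Yes |
| DCR-16w and DCR-24w, all scans | Yes | Yes | Depends on later scans | Yes |
| DCR-16w and DCR-24w, scans before switch | No | No | No | Yes |
| Enters DoR | Unclear | No | No | Yes |

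Reading across:

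1. **Best response.** P is a non-responder for ORR and PR in the best-response table if section 8.4.1.1 is followed.
2. **DCR-16w and DCR-24w.** P succeeds through the CR or PR route, which carries no duration requirement. Q succeeds through SD held under the next drug.
3. **Plain DCR.** It differs only for R. For P and Q the week 8 scan before the switch already gives SD, and that is enough.
4. **DoR.** By section 8.4.1.3, P has a documented response and so could have a DoR. By Table 12 and section 8.5.3.5, DoR belongs to objective responders, which can be read as the ORR responders. S shows that letting an existing response run past the switch is consistent with PFS and is not a fault.

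**Size, as illustration only.** Let k be the patients in an arm who first respond after a switch. With 385 per arm (section 8.2), the gap between best-response CR plus PR and ORR is k/385. The documents do not give k. Assume about 1%, 3% and 5% of the arm:

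- k = 4: 4/385 = 1.0 point
- k = 12: 12/385 = 3.1 points
- k = 19: 19/385 = 4.9 points

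With an assumed 38 ORR responders (38/385 = 9.9%), CR plus PR becomes 42/385 = 10.9%, 50/385 = 13.0% and 57/385 = 14.8%. The odds of response rise by:

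- (42/343)/(38/347) = 1.12
- (50/335)/(38/347) = 1.36
- (57/328)/(38/347) = 1.59

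For an assumed ORR near 5% the factors run from 1.22 to 2.11, and near 18% from 1.07 to 1.36. With one window for both, the gap is 0 by construction.

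**The case against.** The best defence is that the all-assessments rule is a deliberate choice. It fits the intention-to-treat principle and the PFS definition, and a specific ORR rule may override a general one. The window for best response is the kind of derivation detail that the SAP, which is not among the documents, may settle. The DCR endpoints are reported as n (%) per arm, DoR has no formal comparison and best response no formal analysis. ORR, the response endpoint with an odds ratio and p-value, already has the exclusion.

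Much of this stands. It limits the importance of the point and means that the primary OS analysis and its error control are not involved. It does not remove the point, because the protocol is not silent. It states a rule, reverses it for one endpoint, and in section 5.1 gives best response a meaning that the rule does not protect. A SAP that applied the ORR window to best response would depart from section 8.4.1.1. A SAP that followed section 8.4.1.1 would disagree with ORR.

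Three stronger readings are tempting but not supported:

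- **DoR is computed in patients who are not ORR responders.** Table 12 and section 8.5.3.5 allow the opposite reading, so the text is ambiguous rather than wrong.
- **Plain DCR is inflated like the others.** With no minimum SD duration, one evaluable scan without progression before the switch suffices.
- **DCR-16w is overstated by a known amount.** Multiplying an assumed switching share by an assumed share still controlled gives, for example, 0.05 × 0.5 = 2.5 points to 0.15 × 0.8 = 12 points. The documents give neither share, and the product includes patients already in response before the switch, who count anyway. With 1 to 4 points assumed in the other arm, the difference runs from 2.5 − 4 = −1.5 to 12 − 1 = +11 points, so even its direction is open.

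**Conclusion.** The point holds as a minor inconsistency in the Investigator-assessed response endpoints. The text lets a response, or stable disease, seen only after a switch count in best response, DCR-16w and DCR-24w while the same patient is a non-responder for ORR. Plain DCR is exposed only through patients with no evaluable scan before the switch. Entry into DoR needs clarifying.

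That a gap can arise follows from the text. Its size does not: the 1.0 to 4.9 points rest on an assumed 1% to 5% of an arm responding only after a switch. A reader might infer that other drugs' effects will materially favour one arm, but nothing in the documents shows that switching will be frequent or unequal.

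**What to change.** In section 8.4.1.1, qualify the all-assessments rule with an exception for the response endpoints. In section 8.4.1.3, state one data window, up to progression or the start of subsequent anticancer therapy, whichever comes first. Apply it to ORR, best response, DCR, DCR-16w, DCR-24w, and to who qualifies as a responder for DoR.

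Keep PFS, TTP and the DoR end date regardless of subsequent therapy. Excluding later scans from DoR altogether would break the requirement in section 8.4.1.3 that the end of response coincides with the PFS date, so the change to DoR must be confined to entry.

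The cost is a sentence or two and one derivation flag, with the SAP worded to match. DCR-16w and DCR-24w may be slightly lower, because stable disease carried past week 16 or 24 only under another drug would no longer count.
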